2.7 Interim Analyses

The percent of subjects who achieved the primary endpoint will be tested at various time points. As soon as approximately 95% of the subjects (from at least 50 subjects) will be found seroprotected (having anti-HBs antibody concentrations $\geq 10\text{mIU/ml}$) then the primary efficacy endpoint will be achieved and the analysis will be considered a formal interim analysis and will be reported. A second interim analysis will be performed after all subjects have completed all three injections. Subjects who early terminated the study but reached the primary endpoint prior to termination will be included in the analysis.

Interim analysis reports will include all efficacy and safety information collected up to the interim analysis cut-off date. Exploratory endpoints (anti-pre-S1 and anti-pre-S2 testing) will not be included in the interim reports.

2.8 Final Analyses

The final analysis will include all the subjects who completed 12 months of follow-up, fully comply with the study protocol and have no inclusion/exclusion criteria violation. Subjects who early terminated the study but achieved the primary endpoint prior to withdrawal will be included as well (mITT population). If 95% of the subjects will be found seroprotected (having anti-HBs antibody concentrations $\geq 10\text{mIU/ml}$) then the primary endpoint will be achieved.

3. STATISTICAL METHODS

3.1 General

The overall significance level for this study will be 5% using two-tailed tests.

The data will be analysed using the SAS ® version 9.3 or higher (SAS Institute, Cary North Carolina).

3.2 Data Summaries

All measured variables and derived parameters will be listed individually and, if appropriate, tabulated by descriptive statistics.

3.3 Continuous

For continuous variables summary tables will be provided giving sample size, arithmetic mean, standard deviation, standard error, median, minimum and maximum and 95% confidence interval for means (if appropriate). Summary statistics of Anti-HBs antibody concentrations

and Anti-PreS1 and Anti-PreS2 antibodies concentrations will use geometric means due to the expected dispersion and skewness of the data.

3.4 Categorical

For categorical variables summary tables will be provided giving sample size, absolute and relative frequency.

3.5 Protocol Deviations

Listing of protocol deviations will be provided.

4. ANALYSIS PLAN

4.1 Introduction

All summaries and analyses documented below will be presented in the final integrated statistical/clinical report and tables that will be based on the E3 guidelines published by ICH. However, it is noted here that no analysis plan prepared in advance of database lock can be absolutely definitive and so the final report may contain additional tables or statistical tests if warranted by the data obtained. The justification for any such additional analyses will be fully documented in the final report.

Descriptive statistics for each of the study endpoints will be provided for the mITT Analysis Set and for both mITT and FT analyses set for the primary endpoint only.

4.1 Disposition of Subjects

Data from subjects who are screened but not treated, subjects in the ITT, mITT, FT analysis sets, as well as study withdrawal data will be summarized using descriptive statistics. This summary will include all subjects screened into the study. The denominator for calculating the percentages will be the set of the ITT.

4.2 Demographics and Baseline Characteristics

Demographic and baseline data as well as disease prognostic factors, medical history and prior medications will be summarized for the ITT analysis set using appropriate descriptive statistics. Baseline characteristics (age, BMI and smoking status) will be presented by categories used for efficacy analyses. Categories for missing data will be presented if necessary. Missing categories will be presented if necessary.

The proportion of subjects who recorded concomitant medications will be tabulated

4.3 Compliance

Summary table of compliance data based on Sci-B-Vac injections will be generated for the ITT analysis set.

4.4 Primary Endpoint Analysis

The primary endpoint of the study is the Seroprotection rate (SPR), defined as the proportion of subjects with anti-HBs antibody titer at least equal to 10mIU/ml, at Month 7 (i.e. one month after the third immunization with Sci-B-Vac™). In the first Interim Analysis the primary endpoint will be tested on month 4. Subjects early terminated from the study for any reason at any time while having an anti-HBs antibody concentrations ≥ 10 mIU/ml will be considered among those who met endpoint.

The principal analysis of the primary endpoint will employ a non-inferiority analysis [SAS PROC FREQ with binomial (noninf margin=0.09 p=(1- α) exact)] statement will be used for testing the below hypothesis:

H0: $P-p_0 \leq -\text{Margin}$

H1: $P-p_0 > -\text{Margin}$

Where p_0 , the assumed true SPR is 95% and the non-inferiority margin is 9.0%, employing that study will be considered successful if the lower bound of the (1- α) exact CI will be 86.0% or more.

The rate of responders will be calculated along with 95% confidence interval using Exact binomial method. The final population for statistical analysis will include only subjects who fully comply with the study protocol, have no inclusion/exclusion criteria violation and subjects who early terminated the study but reached the primary endpoint prior to withdrawal (mITT population).

Comparative analysis will be applied for baseline characteristics (such as gender, smoking status, age and BMI) between non seroprotected subjects (i.e. anti-HBsAg antibody<10), seroprotected subjects (ie. anti-HBsAg antibody ≥ 10 mIU/ml) and subjects with Anti-HBs ≥ 100 mIU/ml.

Age categories will be defined by intervals of 5 or 10. BMI will be defined <25 or ≥ 25 . Smoking status will be defined using 5 categories:

Never

Past-smoker;

Light smoker (up to 10 cigs/day)

Moderate smoker (10-19 cigs/day)

Heavy smoker (20 or more cigs/day) BMI categories will be defined <25 and ≥ 25

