4.5 Secondary Endpoints Analysis

The secondary endpoints for the study are:

- SPR one month after the first injection and at every month until Month 6 inclusive and at months 9 and 12.
- Percentage of subjects with anti-HBs antibodies titer ≥ 100
- mIU/ml one month after the first injection and then at every month until Month 7 inclusive and at months 9 and 12.
- The geometric mean concentration (GMC) as determined by anti-HBsAg antibody titers at Month 0, then at every month until Month 7 inclusive and at months 9 and 12.

SPR at all time-points as defined above will be analyzed using the principal analysis method as defined for the primary endpoint, and will be presented graphically as well.

The percentage of subjects with anti-HBs antibodies titer ≥ 100 mIU/ml will be calculated from the responders sub-set at each available time-point. Subjects with titer >10 mIU/ml and <100 mIU/ml will be defined 'low-responders'.

The geometric mean concentration (GMC) as determined by anti-HBsAg antibody titers one month after the first injection and at every month until Month 7 inclusive and at months 9 and 12 will be calculated with 95% confidence intervals. Graphical presentation of GMC by month will be generated.

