5. APPENDIX I: TABLES TO BE INCLUDED IN THE STATISTICAL REPORT

Table number	Table Title
14.1	Demographic and Baseline Data
14.1-1.1	Disposition of subjects
14.1-1.2	Primary reason for early discontinuation
14.1-2.1	Analysis population
14.1-3.1	Demographic and Baseline data, ITT
14.1-4	Medical History, ITT
14.1-5	Baseline Physical Examination, ITT
14.1-6	Any Concomitant Medication, ITT
14.1-7	Any Concomitant Non-drug Medication, ITT
14.1.2	Exposure to Sci-B-Vac injection
14.1.2.1	Sci-B-Vac injection, ITT
14.2	Efficacy Analysis
14.2-1	Seroprotection rate (SPR) by Month, mITT
14.2-2	Seroprotection rate (SPR) by Month, FT (for first IA mITT who completed month 7 will be presented)
14.2-3	Secondary Endpoint Analysis: Percentage of Subjects with Anti-HBs \geq 100 mIU/ml by Month, mITT
14.2-4	Secondary Endpoint Analysis: Percentage of Subjects with Anti-HBs \geq 100 mIU/ml) by Month, FT (for first IA mITT who completed month 7 will be presented)
14.2-5	Geometric means of anti-HBs antibody titers by month, mITT
14.2-6	Geometric means of anti-HBs antibody titers by month, FT (for first IA mITT who completed month 7 will be presented)
14.2-7	Frequency of gender by responders (SPR) (at month 4 for first IA)
14.2-8	Frequency of age categories by responders (SPR) (at month 4 for first IA)
14.2-9	Frequency of Responders (SPR) by Smoking status and month (month 4 for IA)
14.2-10	Frequency of Responders (SPR) by BMI categories and month (at month 4 for first IA)
14.2-11	Geometric means of anti-HBs antibody titers by month and Gender
14.2-12	Geometric means of anti-HBs antibody titers by month and age categories
14.2-13	Geometric means of anti-HBs antibody titers by month and Smoking status
14.2-14	Geometric means of anti-HBsAg antibody titers by month and BMI categories
14.2-15	Serologic Markers for Hepatitis B Infection, ITT
14.3	Safety Data
14.3.1	Adverse Events
14.3.1	Summary Incidence of TEAE (Treatment Emergent Adverse Events), ITT
14.3.1-1	Summary of Adverse Events by SOC and PT, ITT

Table number	Table Title
14.3.1-2	Summary of Adverse Events by SOC and PT and Severity, ITT
14.3.1-3	Summary of Adverse Events by SOC and PT and Relation to study drug, ITT
14.3.1-4	Summary of Serious Adverse Events by SOC and PT, ITT
14.3.2	Listing of SAEs (if applicable)
14.3.2-1	Listing of Serious Adverse Events
14.3.4	Abnormal Laboratory Results
14.3.4-1	Incidence of Hematology Abnormal Clinically Significant Results
14.3.4-2	Out of Range Hematology Results

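### SAP 4.4 compares baseline characteristics across overlapping titre groups (<10, ≥10, ≥100 mIU/ml), which dilutes the ≥10 versus ≥100 contrast and makes a test that assumes independent groups conservative

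*SAP*

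**What the plan says.** SAP 4.4 plans that "Comparative analysis will be applied for baseline characteristics (such as gender, smoking status, age and BMI) between non seroprotected subjects" (<10 mIU/ml), seroprotected subjects (≥10 mIU/ml) "and subjects with Anti-HBs ≥ 100 mIU/ml". It names no test, model or pairwise contrast and gives no purpose for the comparison. SAP 3.1 sets only a general 5% two-tailed level.

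SAP 4.5 treats the ≥100 class as part of the responders: its percentage "will be calculated from the responders sub-set at each available time-point". The same section has a separate intermediate class: "Subjects with titer >10 mIU/ml and <100 mIU/ml will be defined" low-responders. SAP 4.4 does not refer to it.

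SAP Appendix I lists the matching tables by seroprotection status only, for example "Frequency of gender by responders (SPR) (at month 4 for first IA") in Table 14.2-7 and "Frequency of Responders (SPR) by BMI categories and month (at month 4 for first IA") in Table 14.2-10. No title among Tables 14.2-7 to 14.2-10 names a ≥100 group. Tables 14.2-11 to 14.2-14, and Figures 5 to 8 in Appendix III, give geometric mean titres by month and by gender, age, smoking and BMI. Figure 2.1 plans three classes (non-responder, responder, high-responder).

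For smoking, SAP 4.4 has "Light smoker (up to 10 cigs/day") followed by a moderate class of 10 to 19 a day.

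**The concern.** The second and third groups are nested, so a programmer who follows SAP 4.4 literally enters the same subjects twice. The usual comparative tests assume that each subject belongs to one group. The ≥10 group is also a mixture of low and high responders and, if most responders are high, its profile is close to that of the ≥100 group whatever the low responders look like. A characteristic that separates weak from strong responders could then be reported as showing no difference.

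Two boundaries have a related fault. A subject smoking exactly 10 cigarettes a day fits both the light and the moderate class. A titre of exactly 10 mIU/ml is seroprotected under SAP 4.4 but falls outside the >10 limit for low-responders in SAP 4.5, so it belongs to no response class.

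**Working it through.** **Inputs.** Evaluable n = 70 and expected seroprotection rate (SPR) 95% (SAP 2.6); 5% two-tailed (SAP 3.1); groups from SAP 4.4. Not in the documents: f, the share of seroprotected subjects with a titre of 10 to <100. It is assumed to lie between 5% and 50%.

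**The plan's own figure.** The SAP gives no figure for this comparison. Its design statement reproduces: 66 of 70 has an exact lower bound of 0.874 (one-sided 95%) or 0.8601 (two-sided 95%), both at or above 86.0%. At SPR 95%, 70 × 0.05 = 3.5, so 3 or 4 subjects are expected below 10. The illustration uses 4 below and 66 at or above.

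**Dilution.** The ≥10 group is a mixture, with mean = f × mean(low) + (1 − f) × mean(high). Therefore

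mean(≥10) − mean(≥100) = f × [mean(low) − mean(high)].

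The contrast keeps the fraction f and loses 1 − f. For a true low-versus-high difference of 40 percentage points (70% v 30%):

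| Low responders of 66 | f | Expected ≥10 v ≥100 contrast (points) | Share lost |
|---|---|---|---|
| 3 | 0.045 | 1.8 | 95% |
| 7 | 0.106 | 4.2 | 89% |
| 13 | 0.197 | 7.9 | 80% |
| 20 | 0.303 | 12.1 | 70% |
| 33 | 0.500 | 20.0 | 50% |

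**A partial bound on f.** Protocol 1.3 reports, for earlier adult studies, more than 50% of vaccinees above 10,000 mIU/ml after the third dose, and 3.5% non-responders (18/513). If both apply at Month 7, f is below (50 − 3.5)/96.5 = 48%, so at least about half the difference is lost. These data do not bound f at Month 4, which the first interim analysis uses before dose 3.

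**Calibration of ≥10 v ≥100.** With a common variance σ² and 66 seroprotected subjects, the true variance of the contrast is σ²/66 × f/(1 − f). A test that assumes independence uses σ²/66 × (2 − f)/(1 − f). The ratio is f/(2 − f), so the test statistic is the low-versus-high statistic multiplied by √[f/(2 − f)]. At f = 0.5 this is √(0.5/1.5) = 0.577; to reach 1.96 the properly scaled statistic must exceed 1.96/0.577 = 3.4, which has a two-sided probability of about 0.07% under no difference. Simulation gives 0.08%.

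**Simulation.** Pearson chi-square at 5% (an assumption, since the SAP names no test), a binary characteristic, 4,000 runs per setting, and 50% prevalence among the 4 non-seroprotected subjects.

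- No true difference: overlapping three-group test 0.4% to 1.1%; ≥10 v ≥100 0.0% to 0.1%; exclusive three-group test 3.3% to 5.0%.
- Low 70% v high 30%, rejection rate:

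| Low responders of 66 | Overlapping three groups | Exclusive three groups |
|---|---|---|
| 3 | 7% | 34% |
| 7 | 8% | 53% |
| 13 | 8% | 69% |
| 20 | 9% | 81% |
| 33 | 30% | 87% |

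**Contrasts not affected.** <10 v ≥10 and <10 v ≥100 share no subjects, so the overlap does not disturb them.

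**The case against.** The strongest reply is that the defect is one of wording with little reach. SAP 4.4 names no test, so any statement about p-values first has to assume one. Two of the three pairwise contrasts are between disjoint groups. The listed Tables 14.2-7 to 14.2-10 use seroprotection status only, which is a disjoint split. Tables 14.2-11 to 14.2-14 and Figures 5 to 8 already relate each characteristic to the full titre scale without any response groups. The comparison has no part in the success rule, and with 3 or 4 subjects expected below 10, contrasts with that group are weak under any grouping.

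All of this stands, and it rules out three stronger readings that a reader might infer:

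- That the tests in this comparison are invalid across the board. Only a three-group test or a ≥10 v ≥100 test is affected, and the error is conservative: it hides associations and does not create them.
- That nearly all of a real difference is lost. That needs f of roughly 10% or less, a figure the documents do not give.
- That the SAP cannot show which characteristics go with a strong response. The tables of geometric mean titre do so, descriptively.

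The reply does not remove the overlap itself. SAP 4.4 states the groups explicitly and SAP 4.5 confirms the nesting. The tables do not resolve it either: the ≥100 group promised in SAP 4.4 appears in none of the four frequency-table titles, so text and outputs disagree.

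**Conclusion.** The group definition in SAP 4.4 is wrong as written, and the consequence is minor. Every subject at ≥100 mIU/ml is also in the ≥10 group. Any test treating the three groups, or ≥10 and ≥100, as independent would be conservative, with simulated rejection of 0.0% to 1.1% against a nominal 5%. The ≥10 v ≥100 contrast loses 95% to 50% of the low-versus-high difference for f between 5% and 50%.

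The dilution formula is exact. Its size rests on the assumed f, and the rejection rates rest also on the assumed chi-square test, 70 subjects and a 70% v 30% difference. The primary success rule (exact lower bound of 86.0% or more), the contrasts of <10 with either other group, and the tables of geometric mean titre by characteristic are untouched. The smoking and exactly-10 boundaries are small separate slips in the same definitions.

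**What to change.** - SAP 4.4: replace the three groups by <10, 10 to <100 and ≥100 mIU/ml, and carry the same three classes into Tables 14.2-7 to 14.2-10 so that text and outputs agree.
- SAP 4.5: define low-responder as ≥10 and <100 mIU/ml, so that a titre of exactly 10 has a class.
- SAP 4.4, smoking: make the classes exclusive, for example <10, 10 to 19 and ≥20 cigarettes a day, alongside never and past smoker.
- State whether a test is intended. With about 3 or 4 non-seroprotected subjects expected of 70, a descriptive comparison is adequate; if a test is wanted, an exact test suits the small group. Which exact test is a matter of preference.

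The cost is one sentence and one smoking boundary in SAP 4.4, one symbol in SAP 4.5, a line on the test, and the response categories of four tables. The number of tables does not change and no further data are needed.

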4.5 Secondary Endpoints Analysis

The secondary endpoints for the study are:

- SPR one month after the first injection and at every month until Month 6 inclusive and at months 9 and 12.
- Percentage of subjects with anti-HBs antibodies titer ≥ 100
- mIU/ml one month after the first injection and then at every month until Month 7 inclusive and at months 9 and 12.
- The geometric mean concentration (GMC) as determined by anti-HBsAg antibody titers at Month 0, then at every month until Month 7 inclusive and at months 9 and 12.

SPR at all time-points as defined above will be analyzed using the principal analysis method as defined for the primary endpoint, and will be presented graphically as well.

The percentage of subjects with anti-HBs antibodies titer ≥ 100 mIU/ml will be calculated from the responders sub-set at each available time-point. Subjects with titer >10 mIU/ml and <100 mIU/ml will be defined 'low-responders'.

The geometric mean concentration (GMC) as determined by anti-HBsAg antibody titers one month after the first injection and at every month until Month 7 inclusive and at months 9 and 12 will be calculated with 95% confidence intervals. Graphical presentation of GMC by month will be generated.

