10.7.2 Secondary Endpoints and Analyses

The secondary endpoints for the study are:

- SPR at one month after the first injection and at every month until Month 6 inclusive and at months 9 and 12.
- Percentage of subjects with anti-HBs antibodies titer ≥ 100 mIU/ml at Month 0, and then at every month until Month 7 inclusive and at months 9 and 12.
-
- The geometric mean concentration (GMC) as determined by anti-HBsAg antibody titers at Month 0, then at every month until Month 7 inclusive and at months 9 and 12.

SPR at all time points as above defined will be analyzed using the principal analysis method as above defined. The geometric mean concentration (GMC) as determined by anti-HBsAg antibody titers at Month 0, then at every month until Month 7 inclusive and at months 9 and 12 will be displayed across time in order to establish the kinetic of the immunological response during the study.

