2.2 Design

This will be a post-marketing, open-label, single arm study in healthy volunteers who had never been vaccinated with any hepatitis B vaccine and who are HBs antigen, anti-HBc and anti-HBsAg antibodies seronegative.

The study assessments will be performed as described in the study flow chart (See section 2.3).

This study will consist of three periods:

Screening Period (Visit 1: up to 1 month prior to first vaccination)

After signing of the informed consent form (ICF), screening procedures will be carried out as specified in the study protocol.

Treatment and Follow-up Period (Visits 2-8: Months 0-6)

Subject identification number will be assigned to all eligible subjects following assessment of inclusion and exclusion criteria.

All eligible subjects will receive Sci-B-Vac™ vaccine. The treatment phase will include three I.M. doses of Sci-B-Vac™ administered in the deltoid muscle on Month 0, Month 1, and Month 6. Subjects will be followed up for safety evaluations and for efficacy (by anti-HBs, anti-pre-S1 and anti-pre-S2 testing), every month. The previous injection site will be inspected before the second and third administration.

The following assessments will be performed during each treatment visit: recording of AEs and concomitant medications, vital signs and blood tests for quantitative anti-HBs, anti-preS1 and anti-preS2 antibodies and safety assessment (including blood and urine laboratory tests).

Female subjects will also undergo a urine pregnancy before each injection. Vital signs are not required on follow-up visits when vaccine is not administered.

Post-Vaccination Follow-up Period (Visits 9-11: Months 7, 9 and 12)

Additional subject follow-up visits will take place 1, 3 and 6 months after the last vaccine administration. On each visit, subjects will be inquired about AEs and concomitant medications, and blood samples for quantitative anti-HBs, anti-preS1 and anti-preS2 antibodies levels will be drawn. The last visit (Month 12) is a study termination visit in which all subjects will also undergo physical examination, laboratory safety assessments (CBC, blood chemistry and urinalysis), vital signs measurement and a 12-lead ECG. In addition, female subjects will undergo a urine pregnancy test.

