2.3 Study Flow-chart

Visit Number	1	2	3	4	5	6	7	8	9	10	11
Visit Name	Screening	Treatment 1	Treatment 2	Follow-up	Follow-up	Follow-up	Follow-up	Treatment 3	Follow-up	Follow-up	Study Termination
Month (Week) of the Study	-1 ((-4) - 0)	0 (0 ¹)	1(4 ¹)	2(8 ¹)	3(12 ¹)	4(16 ¹)	5(20 ¹)	6(24 ¹)	7(28 ¹)	9(36 ²)	12(48 ²)
Activity											
ICF	X										
Demographics	X										
Inclusion/Exclusion	X	X									
Medical history	X										
Vital signs ³	X	X ⁴	X ⁴					X ⁴			X
Smoking status	X										
Weight, height, BMI	X										
Physical examination	X										X
Blood safety tests ⁵	X	X ⁶	X ⁶					X ⁶			X
Screening serology ⁷	X ⁸										
General urinalysis	X	X ⁶	X ⁶					X ⁶			X
Serum β-HCG	X										
Urine pregnancy test		X ⁶	X ⁶					X ⁶			X
12-lead ECG	X										X
Sci-B-Vac™ injection ⁹		X	X					X			
Local reaction grading		X ¹⁴	X ^{14,15}	X ¹⁵				X ¹⁴	X ¹⁵		
Serologic markers for hepatitis B infection	X ^{8,10}	X ^{6,11}	X ^{6,11}	X ¹¹	X ¹¹	X ¹¹	X ¹¹	X ^{6,11}	X ¹¹	X ¹¹	X ¹²
Serologic response to immunization ¹³		X ⁶	X ⁶	X	X	X	X	X ⁶	X	X	X
Sample for further investigations		X ⁶	X ⁶	X	X	X	X	X ⁶	X	X	X
Adverse Events	Recorded throughout the study										
Concomitant Medications	Recorded throughout the study										

- 1 \pm 3 days (Visit2/Treatment 1 may be performed up to 4 weeks +3 days from screening visit)
- 2 \pm 8 days
- 3 Sitting BP, HR, RR, oral temperature
- 4 Within 60 min before vaccine administration and at 60 (\pm 15) min after vaccination
- 5 CBC, blood chemistry, PT/INR (screening only) - see Appendix B
- 6 Prior to vaccine administration
- 7 Anti HIV (Ab type 1&2), anti-HCV Ab, anti-HAV IgM antibodies, ANA (See Appendix B)
- 8 Positive serology excludes from participation in the study
- 9 One IM injections of 1.0 ml into the deltoid muscle. The previous injection site will be inspected before the second and third administration. Subjects will remain for observation in the CRC for at least 1 hour after injections.
- 10 HBsAg, anti-HBs antibodies (also markers for previous vaccination), total anti-HBc antibodies and IgM anti-HBc antibodies.
- 11 HBsAg only.
- 12 HBsAg, Total anti-HBc antibodies and IgM anti-HBc antibodies
- 13 Anti-HBsAg, anti-preS1 and anti-preS2 antibodies
- 14 Local reaction grading after vaccination
- 15 Local reaction grading of previous vaccine administration and follow up until symptoms resolve

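### SAP 4.5 reuses the Month 7 non-inferiority test (95% reference, 86% bound) for SPR at Months 1–6, 9 and 12, without justifying those figures for these visits or giving a multiplicity rule

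*SAP*

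**What the plan says.** The secondary SPR endpoints in SAP 4.5 are "SPR one month after the first injection and at every month until Month 6 inclusive and at months 9 and 12". That is Months 1, 2, 3, 4, 5, 6, 9 and 12, eight visits. For all of them the SAP prescribes: "SPR at all time-points as defined above will be analyzed using the principal analysis method as defined for the primary endpoint". Protocol version 2.0, section 10.7.2, has the same rule: "SPR at all time points as above defined will be analyzed using the principal analysis method as above defined".

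The principal method is in SAP 4.4. It names a SAS non-inferiority procedure for a single proportion with margin 0.09, and the rule is that the "study will be considered successful if the lower bound of the (1- α) exact CI will be 86.0% or more". The expected rate of 95% is introduced in SAP 2.6 alongside the Month 7 endpoint, one month after the third dose.

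Doses are "administered in the deltoid muscle on Month 0, Month 1, and Month 6" (SAP 2.2). In the SAP 2.3 flow chart, the immune-response samples at the three vaccination visits carry the footnote "Prior to vaccine administration".

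On error rates, SAP 3.1 says: "The overall significance level for this study will be 5% using two-tailed tests". Neither the SAP nor protocol version 2.0 adds a testing order, an alpha split or a statement that the secondary SPR analyses are descriptive.

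**The concern.** A non-inferiority test means something only if its reference rate and margin belong to the quantity tested. Here both describe the response to the full three-dose course. At Months 1 to 6 the subject has had one or two doses, and the documents give no expected SPR or margin rationale for those visits as secondary endpoints. A pass or fail against 86% there has no stated interpretation.

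Months 9 and 12 follow the full course, so the 86% bound is less out of place. But each is another test at the full level of the same success rule, with nothing saying how the results relate to Month 7 or to the overall level in SAP 3.1.

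What is at stake is the clarity of the report. The objective these endpoints serve is to characterize the immune response over time (SAP 2.1). Estimates with intervals do that. A run of pass/fail results against a borrowed benchmark does not, and it blurs which test decides whether the batch qualifies.

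**Working it through.** **Inputs.** Bound 95% − 9% = 86% (SAP 4.4). Evaluable n = 70 (SAP 2.6). Enrolment 84 (protocol version 2.0, 5.1) or up to 92 (SAP 2.4). SAP 4.4 gives α no value. SAP 2.6 uses a 95.0% exact CI in the success rule but a one-sided 95.0% CI in the justification. I take the two-sided 95% interval, in line with SAP 3.1, and note where the choice matters.

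**Formulas.** Exact lower bound for x of n: the a-quantile of Beta(x, n − x + 1), with a = 0.025 (two-sided 95%) or 0.05 (one-sided 95%). Pass probability: P(X ≥ r), X ~ Binomial(n, p), where r is the smallest x whose bound reaches 86%.

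**1. The plan's own figure, n = 70.**

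| x/70 | Observed | Two-sided 95% bound | One-sided 95% bound |
|---|---|---|---|
| 65 | 92.9% | 84.11% | 85.57% |
| 66 | 94.3% | 86.01% | 87.40% |
| 67 | 95.7% | 87.98% | 89.29% |

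The stated 86.0% reproduces, and r = 66 under either reading.

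**2. One test at the boundary.** P(X ≥ 66 | n = 70, p = 0.86) = 0.0249.

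**3. Months 7, 9 and 12 together.** Assume a true SPR of 86% at all three visits and n = 70.

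- Independent visits: 1 − (1 − 0.0249)³ ≈ 0.073.
- Repeated titres in one subject are correlated. I modelled each subject with a latent normal variable per visit, cut to give 86% seroprotected, with a common correlation between visits (400,000 simulated trials each). Correlations of 0.5, 0.8 and 0.9 gave 6.9%, 6.3% and 5.6%.

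The chance of at least one pass is therefore about 5.6% to 7.3%, against 2.5% for Month 7 alone.

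**4. Early visits.** The documents give no expected SPR for Months 1–6 as secondary endpoints, so the rates below are assumptions spanning a range. With n = 84 the two-sided rule needs 79 (78/84 gives 85.1%; 79/84 gives 86.7%).

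| Assumed true SPR | P(X ≥ 79 of 84) |
|---|---|
| 70% | 5 × 10⁻⁸ |
| 80% | 0.03% |
| 90% | 14% |
| 92% | 33% |
| 95% | 76% |

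The choice of n or interval does not change the picture. With n = 92 the two-sided rule needs 86, and the pass probability is 0.03% at 80% and 82% at 95%. With the one-sided bound at n = 84 the rule needs 78, giving 0.1% and 87%.

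**The case against.** The strongest reply is that nothing hangs on these tests. The wording that the study succeeds is in the primary-endpoint section, and that endpoint is Month 7. The SAP's table and figure lists show SPR by month, with no secondary pass/fail or p-value table, and SAP 4.4 already asks for the responder rate with an exact 95% interval. Unadjusted secondary analyses without a claim are common. All of this stands, and it limits the weight of the point. It does not make the prescribed method suitable: the text still calls for a hypothesis test with a benchmark taken from another visit.

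A reader might also infer three stronger things that the documents do not support.

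- **That the SAP never asks a 95% question before dose 3.** It does. SAP 4.4 tests the primary endpoint on Month 4 at the first interim analysis, and SAP 2.7 treats the endpoint as achieved once about 95% of at least 50 subjects are seroprotected. Those are interim provisions. They give no rationale for the benchmark as a secondary analysis at Months 1–6.
- **That the early tests are bound to fail.** This holds only if early SPR is well below 86%. At 90% to 95% the outcome is open, as the table shows.
- **That a pass at Month 9 or 12 could rescue a failed Month 7.** No passage says so.

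**Conclusion.** The point holds as a matter of method and reporting. SAP 4.5 and protocol 10.7.2 apply a test built for Month 7 to eight other visits, six of them before any response to the third dose. They justify neither the reference nor the margin there and do not say how the tests relate to the overall 5% level.

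The 5.6% to 7.3% figure shows that the three post-course tests together do not hold the 2.5% of Month 7 alone, nor 5%. It rests on a true SPR of exactly 86% at all three visits and 70 subjects, and it is an illustration rather than a forecast. The documents do not say whether the overall level was meant to cover secondary analyses.

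Counting all eight secondary visits as independent at 86% would give 1 − (1 − 0.0249)⁸ ≈ 18%. That should not be read as the plan's error rate, because repeated titres are correlated and nothing suggests SPR is 86% at every visit.

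At the early visits false passes are rare if SPR is low, and the problem is mainly one of interpretation. The primary Month 7 analysis is not undermined by this point.

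**What to change.** In SAP 4.5, and in the matching sentence of protocol 10.7.2, replace the reuse of the principal method with text such as:

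> SPR at Months 1–6, 9 and 12 will be estimated with exact two-sided 95% confidence intervals. No hypothesis is tested in these secondary analyses, and the 86% success rule is not applied to them.

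Reconcile this with the SAP 4.4 sentence that tests the primary endpoint on Month 4 at the first interim analysis. The new text is worded for the secondary analyses because a statement that the 86% rule applies at Month 7 only would contradict that sentence while it stands.

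The cost is one statement in each document plus that reconciliation. The listed SPR-by-month tables and figures can stay. The sponsor gives up a formal non-inferiority claim at Months 9 and 12, which no stated objective requires.
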